8.5.3 Analysis of Primary Endpoint

Paired t test will be used to evaluate the primary endpoint. The null hypothesis is that there is no difference between MFR at baseline and MFR after twelve week treatment. The alternative hypothesis is that the MFR after twelve week treatment is higher.

Furthermore, the mean value, standard deviation and two-sided 95% confidence interval (CI) will be calculated for the difference between MFR at baseline and after twelve week treatment.

This analysis will be done both in ITT population and PP population.

8.5.4 Analysis of Secondary Endpoints

For secondary endpoints such as MBF by rest PET, MBF by stress PET, ejection fraction (EF%), left ventricular end-systolic dimension (LVESD), left ventricular wall thickness, E/A ratio, paired t test will be used to compare the difference of these parameters between baseline and after twelve week treatment directly, furthermore, 95% confidence interval will also be calculated.

The Seattle angina questionnaire (SAQ) score will be classified into five dimensions: physical limitation (question 1), anginal stability (question 2), anginal frequency (question 3-4), treatment satisfaction (question 5-8) and disease perception (question 9-11). The sum of score in each dimension will be calculated respectively, and then transformed into the standard score between 0 and 100:

$$\frac{(\text{Sum of score} - \text{the minimum value of score in this dimension})}{(\text{the range of score in this dimension})} \times 100$$

For example:

Suppose the sum of score in dimension 1 is 43, and the minimum and maximum of score in this dimension is $1 \times 9 = 9$ and $6 \times 9 = 54$ respectively. So the standard score in this dimension is

$$\frac{43-9}{54-9} \times 100 = 75.55;$$

Suppose the sum of score in dimension 2 is 2 and the minimum and maximum of score in this dimension is 1 and 5 respectively. So the standard score in this dimension is $\frac{2-1}{5-1} \times 100 = 25$

The paired t test will be used to compare the difference of standard score in each dimension, furthermore, the 95% confidence interval will also be calculated.

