7.3.3 Seattle angina questionnaire

1. The Seattle Angina Questionnaire is designed to quantify the physical and emotional effects of coronary artery disease. This instrument (Appendix II) is a 19-item self-administered questionnaire resulting in five scales that measure clinically important dimensions of coronary artery disease: physical limitation, anginal stability, anginal frequency, treatment satisfaction and disease perception;
2. The Seattle Angina Questionnaire is scored by assigning each response an ordinal value, beginning with 1 for the response that implies the lowest level of functioning, and summing across items within each of the five scales. Scale scores are then transformed to a 0 to 100 range by subtracting the lowest possible scale score, dividing by the range of the scale and multiplying by 100. Because each scale monitors a unique dimension of coronary artery disease, no summary score is generated.
3. The Seattle Angina Questionnaire could be finished by a single page of paper. The answers will be copied in the eCRF by investigators as soon as it is completed. It is designed to be self-administered. For patients who can't read, investigators or other family persons could read the questions for them, then the patients could choose the most appropriate answers which the questioners tick them in the paper for the patients. For those who could read, they should complete it by themselves

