Appendix II

The Seattle Angina Questionnaire

1. The following is a list of activities that people often do during the week. Although for some people with several medical problems it is difficult to determine what it is that limits them, please go over the activities listed below and indicate how much limitation you have had **due to chest pain, chest tightness, or angina over the past 4 weeks.**

Place an x in one box on each line.

Activity	Severely Limited	Moderately Limited	Somewhat Limited	A Little Limited	Not Limited	Limited, or did not do for other reasons
Dressing yourself						
Walking indoors on level ground						
Showering						
Climbing a hill or a flight of stairs without stopping						
Gardening, vacuuming, or carrying groceries						
Walking more than a block at a brisk pace						
Running or jogging						
Lifting or moving heavy objects (e.g. furniture, children)						
Participating in strenuous sports (e.g. swimming, tennis)						

2. Compared with 4 weeks ago, how often do you have **chest pain, chest tightness, or angina** when doing your **most strenuous** level of activity?

I have had **chest pain, chest tightness, or angina**...

Much more often	Slightly more often	About the same	Slightly less often	Much less often
				

3. Over the past 4 weeks, on average, how many times have you had **chest pain, chest tightness, or angina**?

I get **chest pain, chest tightness, or angina**...

4 or more times per day	1-3 times per day	3 or more times per week but not every day	1-2 times per week	Less than once a week	None over the past 4 weeks
					

4. Over the past 4 weeks, on average, how many times have you had to take nitros (nitroglycerin tablets) for your **chest pain, chest tightness, or angina**?

I take nitros...

4 or more times per day	1-3 times per day	3 or more times per week but not every day	1-2 times per week	Less than once a week	None over the past 4 weeks

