					

5. How bothersome is it for you to take your pills for **chest pain, chest tightness or angina** as prescribed?

Very bothersome	Moderately bothersome	Somewhat bothersome	A little bothersome	Not bothersome at all	My doctor has not prescribed pills
					

6. How satisfied are you that everything possible is being done to treat your **chest pain, chest tightness, or angina**?

Not satisfied at all	Mostly dissatisfied	Somewhat satisfied	Mostly satisfied	Highly satisfied
				

7. How satisfied are you with the explanations your doctor has given you about your **chest pain, chest tightness, or angina**?

Not satisfied at all	Mostly dissatisfied	Somewhat satisfied	Mostly satisfied	Highly satisfied
				

8. Overall, how satisfied are you with the current treatment of your **chest pain, chest tightness, or angina**?

Not satisfied at all	Mostly dissatisfied	Somewhat satisfied	Mostly satisfied	Highly satisfied
				

9. Over the past 4 weeks, how much has your **chest pain, chest tightness, or angina** interfered with your enjoyment of life?

It has **severely**
limited my
enjoyment of
life

It has
moderately
limited my
enjoyment of life

It has **slightly**
limited my
enjoyment of
life

It has **barely**
limited my
enjoyment of
life

It has **not**
limited my
enjoyment of
life

10. If you had to spend the rest of your life with your **chest pain, chest tightness, or angina** the way it is right now, how would you feel about this?

Not satisfied
at all

Mostly
dissatisfied

Somewhat
satisfied

Mostly
satisfied

Highly
satisfied

i i. How often do you worry that you may have a heart attack or die suddenly?

I can't stop
worrying
about it

I often think
or worry
about it

I occasionally
worry about it

I rarely think
or worry
about it

I never think
or worry
about it

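### The SAQ physical-limitation score ranks the other-reasons box above Not Limited, so an unlimited patient scores 80 out of 100 and a real improvement can score as zero or as worsening

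*Protocol*

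**What the plan says.** Protocol section 7.3.3 gives the coding rule for the Seattle Angina Questionnaire: each response takes an ordinal value, "beginning with 1 for the response that implies the lowest level of functioning". Items are summed within each scale, and the sum is put on a 0 to 100 range by "subtracting the lowest possible scale score, dividing by the range of the scale and multiplying by 100".

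Section 8.5.4 repeats the formula, assigns question 1 to physical limitation, and illustrates it with a case that begins "Suppose the sum of score in dimension 1 is 43, and the minimum and maximum of score in this dimension is". The lower limit it then sets is nine items scored 1, a total of 9; the upper limit is nine items scored 6, a total of 54. A sum of 43 is given a standard score of 75.55. Each dimension's standard score is then compared between baseline and week 12 by a paired t test with a 95% confidence interval.

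Appendix II, question 1, lists nine activities and asks about limitation due to chest pain, chest tightness or angina. Each line has six boxes. The first five run from Severely Limited to Not Limited. The sixth reads "Limited, or did not do for other reasons". Question 5 also has a sixth box outside its graded levels: "My doctor has not prescribed pills".

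Nothing in the protocol sets either of these boxes to missing.

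**The concern.** A maximum of 6 per item means that all six boxes are treated as ordered levels. The sixth box is not a level of angina limitation. It says that something other than angina explains the limitation, or that the activity was not done. Placing it above Not Limited breaks the ordinal rule of section 7.3.3.

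The SAQ is the trial's instrument for symptoms and quality of life (section 5.1.1). Question 1 includes running, heavy lifting and strenuous sports, which patients aged up to 70 may plausibly not do for reasons other than angina. With 11 to 20 patients, a few wrongly ordered answers can move the mean change. The paired t test on this dimension could then miss or reverse a benefit.

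**Working it through.** **Inputs.** Nine items, minimum 9 and maximum 54 (section 8.5.4); box order 1 to 6 (Appendix II, question 1); ascending codes (section 7.3.3).

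**The protocol's own figure.** (43 − 9)/(54 − 9) × 100 = 75.56, which the protocol truncates to 75.55. It reproduces.

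**Ends of the scale under the protocol rule.**
- Nine items Not Limited: (45 − 9)/45 × 100 = 80.0.
- Nine items in the sixth box: (54 − 9)/45 × 100 = 100.0.
- Six items Severely Limited and three in the sixth box: (6 + 18 − 9)/45 × 100 = 33.3. The six angina-rated items alone would score 0.

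**The five graded levels only.** With all nine items answered, the range is 9 to 45, a width of 36. Nine items Not Limited score (45 − 9)/36 × 100 = 100. A sum of 43, for example seven items at 5 and two at 4, scores (43 − 9)/36 × 100 = 94.4. One item step is worth 100/36 = 2.78 points, against 100/45 = 2.22 under the protocol.

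**Change between visits.** The cases below are constructed. The third column scores items 1 to 5 on those answered at each visit, as (mean − 1)/4 × 100. The last column uses only the items answered at both visits.

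| Case | Protocol score | Answered items, 1 to 5 | Items answered at both visits |
|---|---|---|---|
| A. Six items 4 to 5; three items box 6 to 4 | sums 42 and 42: 73.3 to 73.3 (0) | 75.0 to 91.7 (+16.7) | 75 to 100 |
| B. Six items 3 to 4; three items box 6 to 3 | sums 36 and 33: 60.0 to 53.3 (−6.7) | 50.0 to 66.7 (+16.7) | 50 to 75 |
| C. Six items stay at 5; three items box 6 to 4 | sums 48 and 42: 86.7 to 73.3 (−13.3) | 100 to 91.7 (−8.3) | 100 to 100 |
| D. Eight items stay at 4; one item box 6 to 5 | sums 38 and 37: 64.4 to 62.2 (−2.2) | 75.0 to 77.8 (+2.8) | 75 to 75 |

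One patient with three items moving from box 6 to 4 loses 13.3 points on those items. At n = 11 that takes 13.3/11 = 1.2 points off the mean change.

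**If nobody ticks the sixth box.** The protocol score is exactly 36/45 = 0.8 times the five-level score. Changes and confidence limits shrink to 80%; the t statistic and p-value do not change.

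**The case against.** - **The protocol never says in words that the sixth box scores 6.** True. It follows from the maximum of 54, the printed order and the ascending codes. The other readings do not rescue the scale. If 6 belonged to Not Limited, the sixth box would need a code from 1 to 5 among the angina levels, which is also invalid, although the figure of 80 would no longer apply. If the sixth box were unscored, the maximum would be 45, not 54.
- **The harm is conditional.** This stands. A zero or reversed change requires use of the sixth box to differ between visits. If it is the same at both, the direction is kept and only the size shrinks. The documents give no frequency, so the cases above show what can happen, not what is likely.
- **The fix does not remove every artefact.** This stands. In case C the score still falls by 8.3 when a patient takes up an activity and finds it slightly limiting. That comes from comparing different sets of items, and it is smaller than the 13.3 under the protocol.
- **Scoring on answered items sits awkwardly with section 8.5.2**, which rules out imputation. This is a fair point about wording and is dealt with in the fix.
- **The reach is limited.** Dimension 1 is one of five separately analysed scales. The third secondary objective concerns angina attacks, for which angina frequency (questions 3 and 4) is the closer scale, and the six boxes there are properly ordered. For question 5, section 8.5.4 gives no numerical range, so an error there would arise only if the same rule were applied.

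None of this makes the printed range of 9 to 54 valid.

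**Conclusion.** The concern holds: the physical-limitation scoring is wrong as written. No reading consistent with a maximum of 54 gives a valid scale. Under the printed box order, an unlimited patient scores 80, a patient who ticks the sixth box throughout scores 100, and a sum of 43 from graded answers scores 75.6 instead of 94.4. Lost or reversed improvement is possible wherever use of the sixth box changes between visits; how often that would happen is unknown. Even without any such use, the reported effect is 80% of its size on the five-level scale. Because the protocol itself fixes the range, an SAP that follows it inherits the error. The primary endpoint and the sample size are not affected.

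**What to change.** In section 8.5.4:

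- Score question 1 from 1 to 5 and treat the sixth box as not answered.
- Define the score as (mean of answered items − 1)/4 × 100, and set the dimension to missing below a pre-set number of answered items. Five of nine is one possible choice; the protocol offers no figure.
- Replace the maximum of 54 by 45 in the worked example, so that a sum of 43 on nine answered items gives 94.4.
- Treat the sixth box of question 5 as not answered as well. Leave questions 3 and 4 on their six ordered levels.
- State in section 8.5.2 that scoring a scale on its answered items is part of the scoring rule and is not imputation of missing visits.
- Consider a sensitivity analysis restricted to items answered at both visits, which removes the artefact in case C.

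The cost is a wording change and a change to the scoring program. No new data are needed, since the questionnaire answers are copied into the eCRF and can be rescored. A few patients may end up with a missing dimension-1 score.

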8.5.5 Safety Analyses

All safety analyses will be performed on the safety population. AEs will be classified by Primary System Organ Class (SOC) and Preferred Term (PT) according to the Medical Dictionary for Regulatory Activities (MedDRA).

The incidence of treatment-emergent adverse events will be tabulated. In addition, the incidence of treatment-emergent AEs considered related to study medication (i.e., those AEs judged by the investigator to be either certainly, probably or possibly related to study medication and those with missing casual relationship) as well as the incidence of treatment-emergent AEs with severe or very severe intensity will also be reported.

All SAEs and those AEs leading to permanent discontinuation of study medication will be reported.

Summary statistics will be provided for body weight, vital signs, ECG parameters and safety-related laboratory analyses. Summaries will consist of the number of patients assessed, sample mean value observed together with its associated standard error, sample mean change versus baseline together with its associated standard error and 95% confidence interval.

8.5.6 Analysis of Further Endpoints

The MFR results of standard treatment will be shown by subjects.

8.6 Interim Analysis

No formal interim analysis is planned.

9 Ethical and Regulatory Aspects

9.1 Responsibilities of the Investigator

The Investigator is responsible for the conduct of the trial at his/her site. He/she will ensure that the trial is performed in accordance with the clinical trial protocol, the ethical principles that have their origin in the Declaration of Helsinki, the ICH Note for Guidance on Good Clinical Practice (ICH Topic E6, 1996), the Chinese GCP (06/08/2003), and any other

applicable regulations. In particular, the Investigator must ensure that only subjects who have given their informed consent are included in the trial.

9.2 Subject Information and Informed Consent

An unconditional prerequisite for a subject's participation in the trial is his/her written informed consent. The subject's written informed consent to participate in the trial must be given before any trial-related activities are carried out.

Adequate information must therefore be given to the subject by the Investigator before informed consent is obtained (a person designated by the Investigator may give the information, if permitted by local regulations). With the cooperation of the Sponsor, and in accordance with the Note for Guidance on Good Clinical Practice (ICH Topic E6, 1996), the Japanese ministerial ordinance on GCP, and the ethical principles that have their origin in the Declaration of Helsinki, the Investigator will prepare the informed consent form and other written information to be used in obtaining informed consent from the trial subjects. The Sponsor should provide the investigator with documents/information necessary for preparing the aforementioned written information and cooperate with the investigator to prepare it. In addition to providing this written information to a potential subject, the Investigator or his/her designate will inform the subject of all pertinent aspects of the trial orally as well as in writing. The language used in the aforementioned oral and written information about the trial must be fully and readily understandable to lay persons.

Before consent may be obtained, the investigator should provide the prospective subject (the prospective subject's legally acceptable representative in the case of obtaining the consent of the legally acceptable representative) with ample time and opportunity to inquire about details of the clinical trial and to decide whether or not to participate in the trial. In such cases, the investigator or the trial collaborator giving supplementary explanation should answer all questions about the trial to the satisfaction of the prospective subject (or of the prospective subject's legally acceptable representative in the case of obtaining the consent of the legally acceptable representative).

Depending on national regulations, a person other than the Investigator may inform the subject about the trial and sign the Informed Consent Form, as above.

After the information is provided by the Investigator, the Informed Consent Form must be signed and personally dated by the subject and the Investigator.

The signed and dated declaration of informed consent will remain at the Investigator's site and must be safely archived by the Investigator so that the forms can be retrieved at any time for monitoring, auditing and inspection purposes. A copy of the signed and dated information and Informed Consent Form should be provided to the subject prior to participation.

Whenever important new information becomes available that may be relevant to the subject's consent, the Investigator will revise the subject information sheet and any other written information provided to the subjects and submit them to the IRB for review and opinion. Using the approved revised subject information sheet and other written information, the Investigator will explain the changes to the previous version to each trial subject and obtain his/her written consent for continued participation in the trial.

9.3 Subject Identification and Privacy

A unique subject number will be assigned to each subject at inclusion, immediately after informed consent has been obtained. This number will serve as the subject's identifier in the trial as well as in the clinical trial database.

The subject's data collected in the trial will be stored under this number. Only the Investigator will be able to link the subject's trial data to the subject via an identification list kept at the site. The subject's original medical data will be accessible for the purposes of source data verification by the Monitor, audits and regulatory inspections, but the subject's confidentiality will be strictly maintained.

Data protection and privacy regulations will be observed in capturing, forwarding, processing, and storing subject data. Subjects will be informed accordingly, and will be requested to give their consent on data handling procedures in accordance with national regulations. For subject registration, the investigator will fill out the subject registration form completely and send it to the subject registration center by fax.

When it is confirmed that the subject meets all inclusion criteria and does not meet any of the exclusion criteria, the subject registration center registers the subject and informs the Investigator and the Sponsor of the registration number by fax. If the subject is ineligible for the trial and is therefore not given a registration number, a subject number is allocated and documented.

9.4 Emergency Medical Support and Subject Card

Subjects enrolled in this clinical trial will be provided with Emergency Medical Support cards during their trial participation, which will be furnished by the Sponsor. The Emergency Medical Support card is based on the need to provide clinical trial subjects with a way of identifying themselves as participating in a clinical trial, and subsequently to give health care providers access to the information about this participation that may be needed to determine the course of the subject's medical treatment.

This service is designed to provide information to health care providers who are not part of the clinical trial.

Clinical trial Investigators, who are already aware of the clinical trial protocol and treatment, have other means of accessing the necessary medical information for the management of emergencies occurring in their subjects.

The first point of contact for all emergencies will be the clinical trial Investigator caring for the affected subject. The Investigator agrees to provide his or her emergency contact information on the card for this purpose. If the Investigator is available when an event occurs, s/he will answer any questions. Any subsequent action will follow the standard processes established for the Investigators.

In cases where the Investigator is not available, Merck Serono provides the appropriate means to contact a Sponsor physician. This includes the provision of a 24 hour contact number at a call center, whereby the health care providers will be given access to the appropriate Sponsor physician to assist with the medical emergency and to provide support for the subject concerned.

9.5 Clinical Trial Insurance and Compensation to Subjects

The Sponsor is entirely responsible for AEs that are associated with this trial and cause damage to the health of the subjects, except for AEs caused by an intentional and/or significant deviation on the part of the Investigator, the trial site, and/or the subject. The Sponsor takes out insurance to fulfill the responsibility.

Insurance coverage shall be provided for each country participating to the trial. Insurance conditions shall meet good local standards, as applicable.

